## **7 Safety monitoring**

### **7.1 Adverse events**

An adverse event (AE) is any untoward medical occurrence (i.e., any unfavorable and unintended sign [including abnormal laboratory findings], symptom or disease) in a subject or clinical investigation subject *after providing written informed consent* for participation in the study. Therefore, an AE may or may not be temporally or causally associated with the use of a medicinal (investigational) product.

The occurrence of adverse events should be sought by non-directive questioning of the patient at each visit during the study. Adverse events also may be detected when they are volunteered by the patient during or between visits or through physical examination, laboratory test, or other assessments.

Abnormal laboratory values or test results constitute adverse events only if they fulfill at least one of the following criteria:

- they induce clinical signs or symptoms,
- they are considered clinically significant,
- they require therapy.

Clinically significant abnormal laboratory values or test results should be identified through a review of values outside of normal ranges/clinically notable ranges, significant changes from baseline or the previous visit, or values which are considered to be non-typical in patient with underlying disease. Investigators have the responsibility for managing the safety of individual patient and identifying adverse events. Alert ranges for labs and other test abnormalities are included in Appendix 1.

Adverse events should be recorded in the Adverse Events CRF under the signs, symptoms or diagnosis associated with them accompanied by the following information.

- the severity grade
  - mild: usually transient in nature and generally not interfering with normal activities

- moderate: sufficiently discomforting to interfere with normal activities
- severe: prevents normal activities
- its relationship to the (*select what is applicable*) study treatment (no/yes), or investigational treatment (no/yes), or the other study treatment(non-investigational) (no/yes), or both or indistinguishable,
- its duration (start and end dates) or if the event is ongoing an outcome of not recovered/not resolved should be reported.
- whether it constitutes a serious adverse event (SAE)
- action taken regarding study treatment
- whether other medication or therapies have been taken (concomitant medication/non-drug therapy)
- its outcome (not recovered/not resolved; recovered/resolved; recovering/resolving, recovered/resolved with sequelae; fatal; or unknown)

An SAE is any adverse event (appearance of (or worsening of any pre-existing) undesirable sign(s), symptom(s) or medical conditions(s) which meets any one of the following criteria

- is fatal or life-threatening
- results in persistent or significant disability/incapacity
- constitutes a congenital anomaly/birth defect
- requires inpatient hospitalization or prolongation of existing hospitalization, unless hospitalization is for:
  - routine treatment or monitoring of the studied indication, not associated with any deterioration in condition
  - elective or pre-planned treatment for a pre-existing condition that is unrelated to the indication under study and has not worsened since signing the informed consent
  - treatment on an emergency outpatient basis for an event not fulfilling any of the definitions of a SAE given above and not resulting in hospital admission
  - social reasons and respite care in the absence of any deterioration in the patient's general condition
- is medically significant, i.e. defined as an event that jeopardizes the patient or may require medical or surgical intervention to prevent one of the outcomes listed above.

All malignant neoplasms will be assessed as serious under “medically significant” if other seriousness criteria are not met.

**Unlike routine safety assessments, SAEs are monitored continuously and have special reporting requirements; see Section 7.2.**

All adverse events should be treated appropriately. Treatment may include one or more of the following: no action taken (i.e. further observation only); [study/investigational] (*select*) treatment dosage adjusted/temporarily interrupted; study drug(s) permanently discontinued;

concomitant medication given; non-drug therapy given. The action taken to treat the adverse event should be recorded on the Adverse Event CRF.

Once an adverse event is detected, it should be followed until its resolution or until it is judged to be permanent, and assessment should be made at each visit (or more frequently, if necessary) of any changes in severity, the suspected relationship to the study treatment, the interventions required to treat it, and the outcome.

Information about common side effects already known about the investigational drug can be found in the Investigator Brochure (IB) or will be communicated between IB updates in the form of Investigator Notifications. This information will be included in the patient informed consent and should be discussed with the patient during the study as needed.

The investigator should also instruct each patient to report any new adverse event (beyond the protocol observation period) that the patient, or the patient's personal physician, believes might reasonably be related to study treatment. This information should be recorded in the investigator's source documents, however, if the AE meets the criteria of an SAE, it must be reported to Novartis.

## **7.2 Serious adverse event reporting**

To ensure patient safety, every SAE, regardless of causality, occurring after the patient has provided informed consent and until 30 days after the last study visit must be reported to Novartis within 24 hours of learning of its occurrence. Any SAEs experienced after the 4 weeks period should only be reported to Novartis if the investigator suspects a causal relationship to study treatment.

Recurrent episodes, complications, or progression of the initial SAE must be reported as follow-up to the original episode, regardless of when the event occurs. This report must be submitted within 24 hours of the investigator receiving the follow-up information. An SAE that is considered completely unrelated to a previously reported one should be reported separately as a new event.

Information about all SAEs (*either initial or follow up information*) is collected and recorded on the paper Serious Adverse Event Report Form. The investigator must assess the relationship to *each specific component of study treatment (if study treatment consists of several drugs)* complete the SAE Report Form in English, and send the completed, signed form by fax within 24 hours after awareness of the SAE to the local Novartis Drug Safety and Epidemiology Department. The telephone and fax number of the contact persons in the local department of Drug Safety and Epidemiology, specific to the site, are listed in the investigator folder provided to each site. The original copy of the SAE Report Form and the fax confirmation sheet must be kept with the case report form documentation at the study site. Follow-up information should be provided using a new paper SAE Report Form stating that this is a follow-up to a previously reported SAE

Follow-up information provided should describe whether the event has resolved or continues, if and how it was treated, whether the treatment code was broken or not and whether the patient continued or withdrew from study participation. Each re-occurrence, complication, or progression of the original event should be reported as a follow-up to that event regardless of when it occurs.

If the SAE is not previously documented in the Investigator's Brochure or Package Insert (new occurrence) and is thought to be related to the investigational treatment a Drug Safety and Epidemiology Department associate may urgently require further information from the investigator for Health Authority reporting. Novartis may need to issue an Investigator Notification (IN) to inform all investigators involved in any study with the same investigational treatment that this SAE has been reported.

Local Novartis Turkey Drug Safety Department will report all fatal or life-threatening suspected unexpected serious adverse reactions (SUSARs) to Ministry of Health as per The Regulation on Clinical Trials and Guidance on the collection, verification and submission of Adverse Event/Reaction Reports Occurring During Clinical Trials of **Medicinal Products and Biological Products**.

### **7.3 Pregnancy reporting**

To ensure patient safety, each pregnancy occurring while the patient is on study treatment must be reported to Novartis within 24 hours of learning of its occurrence. The pregnancy should be followed up to determine outcome, including spontaneous or voluntary termination, details of the birth, and the presence or absence of any birth defects, congenital abnormalities, or maternal and/or newborn complications.

Pregnancy should be recorded on a Clinical Trial Pregnancy Form and reported by the investigator to the local Novartis Drug Safety and Epidemiology Department. Pregnancy follow-up should be recorded on the same form and should include an assessment of the possible relationship to the study treatment.

Any SAE experienced during pregnancy must be reported on the SAE Report Form.

## **8 Data review and database management**

### **8.1 Site monitoring**

Before study initiation, at a site initiation visit or at an investigator's meeting, a Novartis representative will review the protocol and CRFs with the investigators and their staff. During the study, the field monitor will visit the site regularly to check the completeness of patient records, the accuracy of entries on the CRFs, the adherence to the protocol and to Good Clinical Practice, the progress of enrollment, and to ensure that study treatment is being stored, dispensed, and accounted for according to specifications. Key study personnel must be available to assist the field monitor during these visits.

The investigator must maintain source documents for each patient in the study, consisting of case and visit notes (hospital or clinic medical records) containing demographic and medical information, laboratory data, electrocardiograms, and the results of any other tests or assessments. All information on CRFs must be traceable to these source documents in the patient's file. The investigator must also keep the original informed consent form signed by the patient (a signed copy is given to the patient).

The investigator must give the monitor access to all relevant source documents to confirm their consistency with the CRF entries. Novartis monitoring standards require full verification for the presence of informed consent, adherence to the inclusion/exclusion criteria, documentation of SAEs, and of data that will be used for all primary variables. Additional

checks of the consistency of the source data with the CRFs are performed according to the study-specific monitoring plan. No information in source documents about the identity of the patients will be disclosed.

## **8.2 Data collection**

Designated investigator staff must enter the information required by the protocol onto the Novartis CRFs that are printed on 3-part, non-carbon-required paper. Field monitors will review the CRFs for completeness and accuracy and instruct site personnel to make any required corrections or additions. The CRFs are forwarded to the Medical Documents Reception Center of Novartis *[or CRO working on behalf of Novartis]* by field monitors or by the investigational site, with one copy being retained at the investigational site. Once the CRFs are received by Novartis *[or CRO working on behalf of Novartis]*, their receipt is recorded, the original copy is placed in Central Files, and the non-carbon-required copy is forwarded to the responsible Data Management staff for processing.

## **8.3 Database management and quality control**

Data from the CRFs are entered into the study database by Novartis Data Management staff using single data entry. Verification is performed manually by a separate member of the Data Management staff by comparing the Case Report Form to the data entered into the database.

Data from the CRFs are entered into the study database by Contract Research Organization (CRO) staff following their own internal standard operating procedures that have been reviewed and approved by Novartis.

Subsequently, the entered data are systematically checked by Data Management staff, using error messages printed from validation programs and database listings. Other errors or omissions are entered on Data Query Forms, which are returned to the investigational site for resolution. The signed original and resolved Data Query Forms are kept with the CRFs at the investigator site, and a copy is sent to Novartis so the resolutions can be entered into the database. Quality control audits of all key safety and efficacy data in the database are made prior to locking the database.

Adverse events will be coded using the Medical dictionary for regulatory activities (MedDRA) terminology.

Laboratory samples will be processed centrally and the results will be sent electronically to Novartis (or a designated CRO).

## **8.4 Data Monitoring Committee**

Not required.

## **8.5 Adjudication Committee**

Not required.

## **9 Data analysis**

### **9.1 Analysis sets**

Data analysis will be performed after all of the data is collected from the enrolled patients. All RRMS patients will be accepted as the analysis sets.

The statistical analyses of this study will be performed by a Contract Research Organization

### **9.2 Patient demographics and other baseline characteristics**

Data collected for patient demographics and the baseline characteristics will be summarized by descriptive statistics with summary tables.

### **9.3 Treatments (study drug, rescue medication, other concomitant therapies, compliance)**

Data collected for treatments will be summarized by descriptive statistics with summary tables.

### **9.4 Analysis of Efficacy Variables**

#### **9.4.1 Primary efficacy endpoint:**

The primary end-point was planned as evaluating the effects of Fingolimod on cognitive performance in highly active, RRMS patients comparing cognitive performance at baseline and at Month 24, after treatment for two years as assessed by BICAMS battery test.

In this study, it is proposed to observe an increase of 3 points in SDMT testing (which roughly equals to 5 % increase in SDMT overall score) is meaningful and in our study, with treatment we may expect a 5% increase in cognitive functioning during a considerably longer duration of treatment and follow-up.

#### **9.4.2 Secondary efficacy endpoints:**

The metric for the PASAT assessment is the number of correct answers.

The Stroop test yields three scores based on the number of items completed on each of the three stimulus sheets.

All MRI analysis will be performed at the Kocaeli University Faculty of Medicine which is the center of the study coordinator investigator.

SIENAX—cross-sectional method will be used to measure atrophy. (25)

Whole brain volume, total gray matter volume, cortical gray matter volume and deep gray matter volume will be measured.

White matter lesions will be segmented by using  $k$  nearest neighbor classification with tissue-type priors, The resulting lesion volume will be normalized for head size to create normalized lesion volume (26,27) Lesion filling will be applied to minimize the effect of hypointense lesions on atrophy measurements (28). Normalized whole-brain volume, normalized gray

matter volume (NGMV), and normalized white matter volume (NWMV) will be measured with SIENAX (part of FSL [Functional MRI of the Brain, or FMRIB, Software Library] 5.0.2, <http://www.fmrib.ox.ac.uk/fsl>) by using optimized parameters for brain extraction (29,30).

Deep gray matter volumes will be measured by using FSL FIRST software (31). Cortical thickness will be measured by using FreeSurfer 5.1 software (<https://surfer.nmr.mgh.harvard.edu/>) (32,33). FreeSurfer uses the T1-weighted image to locate the white matter and pial surface. The distance between both surfaces gives the cortical thickness at each location.

Thalamic and intracranial volumes will be segmented automatically. Thalamic volumes and thalamic fractions will be calculated as ratios of the left and right thalamic volume to the intracranial volume.

Correlation between effect of fingolimod on cognitive performances and brain atrophy will be explored.

### **9.4.3 Statistical model, hypothesis, and method of analysis**

The basic hypothesis of the study is improvements in cognitive tests in RRMS patients. The sample size calculation for the study has been based on an improvement with treatment in a cognitive test (SDMT).

#### **9.4.3.1 Data analysis**

##### **General Approach**

All Statistical analyses will be performed with MedCalc Statistical Software version 13.1.2 (MedCalc Software bvba, Ostend, Belgium; <http://www.medcalc.org>; 2014) at the 5% significance level using 2-sided tests or 2-sided Confidence Intervals.

##### Descriptive Statistics

The quantitative variables will be summarized using the following parameters:

- Number of non-missing data (n),
- Mean,
- Standard deviation,
- 2-sided 95% CI of the mean,
- Median,
- Minimum,
- Maximum.

The qualitative variables will be summarized using the following parameters:

- Number of non-missing data (n),
- Counts and percentages.

Missing data or unknown responses will not be counted in the percentages.

##### Comparisons of Two Groups

Student t test will be used for comparisons of two independent normally distributed groups, Mann Whitney u test will be used for comparisons of two independent non-normally distributed groups.

Paired samples t test will be used for comparisons of two dependent normally distributed groups, Wilcoxon Signed Rank test will be used for comparisons of two independent normally distributed groups.

For comparisons of categorical and independent data Chi-Square test or Fisher Exact test (where appropriate) will be used.

To assess categorical and dependent variables Mc Nemar test will be used.

Normality of continuous data will be tested by using Shapiro-Wilk test.

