#### **9.4.3.2 Statistical Methods by Evaluation of Study Objective**

##### **Primary Objective:**

Primary objective of the study will be evaluated by the statistical methods which are stated below:

- Calculated scores of BICAMS (SDMT, CVLT2 and BVMTR) at baseline, 12th month and 24th month will be compared by using Repeated Measures ANOVA (if variables are non-normally distributed Friedman Test).

Post-Hoc comparisons will be done with Tukey test. (if Friedman test was used, Wilcoxon Signed Rank test will be used for Post-Hoc comparisons.)

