#### **9.6 Sample size calculation**

The primary objective of this study was set as investigating the effects of Fingolimod on cognitive performance in highly active relapsing remitting multiple sclerosis (RRMS) patients. Thus the primary end-point was planned as evaluating the effects of Fingolimod on cognitive performance in highly active, RRMS patients comparing cognitive performance at baseline and at Month 24, after treatment for two years as assessed by BICAMS battery test.

The Symbol Digit Modalities Test (SDMT) is one of the best known tests for detecting the cognitive impairment in patients with organic cerebral dysfunctions. The SDMT has a high sensitivity in detecting the presence of brain damage with providing data on cognitive functioning over time in response to treatment. The scoring of SDMT varies between 0-110 and in a study which evaluated age-related cognitive decline, baseline SDMT values for 50-64 years age group was 52.9 and for the 65+age group was 45.9 (34).

There are currently various clinical work is on-going for detection of decremental or incremental changes of cognitive function in RRMS patients and in a recent publication by Benedict et al which evaluated cognitive decline in RRMS patients, the mean SDMT score was found to be 53.1 for stable RRMS patients at baseline. In this study, the authors concluded that the increment of decline on SDMT was 3.5 raw score points, or roughly 6%. It was concluded that in overall, there seems to be an emerging consensus that a score change of 3-4 points on SDMT is clinically meaningful (35).

In this study, it is proposed to observe an increase of 3 points in SDMT testing (which roughly equals to 5% increase in SDMT overall score) is meaningful and in our study, with treatment

we may expect a 5% increase in cognitive functioning during a considerably longer duration of treatment and follow-up.

As per published literature, any cognitive improvement on the basis of SDMT test at a rate of % 5 should be evaluated as a significant improvement for RRMS patient with cognitive dysfunction. Thus, in this study we have postulated to reach a 5 % improvement in SDMT test at 24 months when compared to baseline in the cognitively impaired RRMS patients.

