Thus, on the basis of percentage improvement expected and by setting alpha at 0.05 and without considering power (no treatment group comparisons will be made); a minimum of 73 RRMS patients has been calculated to be enrolled. However, due to debilitating nature of RRMS as a disease and considerably longer duration of treatment and/or follow-up, a 10 % LFU should be expected and for providing coverage for such cases, 80 RRMS patients should be enrolled to the study.

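### A loosely specified Shapiro-Wilk pre-test chooses the primary BICAMS method, and neither the rank branch nor the ANOVA branch asks for the mean change needed to judge a 3-point SDMT gain.

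*Combined protocol and SAP*

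**What the plan says.** Section 9.4.3.1 (Comparisons of Two Groups) sets the pre-test: "Normality of continuous data will be tested by using Shapiro-Wilk test". Comparisons of Several Groups, in the same section, sends normal repeated data to repeated measures ANOVA and non-normal repeated data to Friedman. Section 9.4.3.2 (Primary Objective) applies this to the SDMT, CVLT2 and BVMTR scores at baseline, Month 12 and Month 24: repeated measures ANOVA, or "if variables are non-normally distributed Friedman Test". Post-hoc comparisons are by Tukey on the ANOVA branch and by Wilcoxon signed rank on the Friedman branch. All testing is "at the 5% significance level using 2-sided tests or 2-sided Confidence Intervals".

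The effect of interest is in points. Sections 9.4.1 and 9.6 say that "it is proposed to observe an increase of 3 points in SDMT testing", and section 9.6 adds that "we have postulated to reach a 5 % improvement in SDMT test at 24 months when compared to baseline". No corresponding figure is given for CVLT2 or BVMTR.

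Descriptive Statistics lists the mean with its two-sided 95% CI for quantitative variables but does not mention change from baseline. Section 9.4.4 plans no supportive analyses.

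**The concern.** A comparison of the same patients across visits depends on the distribution of within-patient changes, not on how scores spread between patients. A skewed or mixed population can have well-behaved changes, and the reverse can also occur. The plan never mentions changes or residuals. It speaks of continuous data and variables and then compares calculated scores, so scores by visit are the likely target of the test.

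The rule is also incomplete. Three scores are each measured at three visits. The plan does not say whether one failing visit out of three triggers Friedman, or whether the decision is taken score by score. Two analysts could reach different primary methods from the same data.

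At stake is whether the primary result can be read against the 3-point gain. Friedman and the Wilcoxon follow-up are specified as tests only, and ranks carry no information on points.

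**Working it through.** **Inputs from the documents.** Alpha 0.05 two-sided (section 9.4.3.1). An effect of +3 SDMT points, with a reference baseline: "the mean SDMT score was found to be 53.1 for stable RRMS patients at baseline" (3/53.1 = 5.6%). 73 evaluable and 80 enrolled, with 10% loss (section 9.6). BVMTR is scored 0-12 on each of three trials (section 6.4.1), so the total runs 0-36. No SD, within-patient correlation or BVMTR mean is given, and the size was set "by setting alpha at 0.05 and without considering power (no treatment group comparisons will be made").

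**1. The plan's own sample size.** Section 9.6 names no formula; the size is set "on the basis of percentage improvement expected". A one-proportion precision formula matches: n = z²p(1−p)/d² = 1.96² × 0.05 × 0.95 / 0.05² = 72.99, so 73. For dropout, 73 × 1.1 = 80.3, 73/0.9 = 81.1, and 80 × 0.9 = 72. This formula uses neither the 3 points nor an SD, so every SD below is an assumption.

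**2. Scores versus changes.** Simulated trials with n = 73, Shapiro-Wilk at 5% and assumed shapes:

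| Assumed shape | At least one of three visits flagged | Month 24 minus baseline flagged |
|---|---|---|
| Everything normal, unrounded | 12% | 5% |
| Scores skewed between patients, changes normal | 90% | 5% |
| Mixture of impaired and unimpaired, changes normal | 99% | 5% |
| BVMTR with ceiling at 36 | 99.8% | 15% |
| Scores near normal, changes heavy-tailed | 19% | 64% |

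The paired t test kept its level: 4.8% with normal changes and 5.1% with heavy-tailed ones. In the scenarios without a ceiling, coverage of the 95% CI for the mean change was 94.7-95.3%.

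**3. How often the switch would fire.** Simulated with n = 72, correlation 0.75 and rounded scores. For normal SDMT (SD 12), at least one visit is flagged in about 14-16% of trials; three independent tests would give 1 − 0.95³ = 14%. For BVMTR the rate depends on the assumed mean and SD: 14% at mean 20, SD 6; 42-43% at mean 24, SD 7; 96% at mean 27, SD 7. The BVMTR change is flagged in about 7-15%.

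**4. What the switch costs.** SDMT, true means 0, 1.5 and 3 points at the three visits, SD 12:

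- Friedman always: 62-64%.
- Repeated measures ANOVA always: 75-76%.
- The two-stage rule as planned: about 73%, or about 2 points below ANOVA. Rough check: 0.14 × 63% + 0.86 × 75% = 8.8% + 64.5% = 73.3%.
- Month 24 versus baseline alone: paired t 84%, Wilcoxon 82%.

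For a BVMTR score near its ceiling the switch fires almost always, and the cost is up to about 11 points. Type I error of the two-stage rule was 4.7% for SDMT and 5.0-5.3% for three BVMTR settings.

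**5. Ranks carry no points.** Take 73 patients, 48 improving and 25 worsening by k points at Month 24, and by half of that at Month 12. The mean change is k(48 − 25)/73 = 0.315k, so 0.32, 0.95 and 1.89 points for k = 1, 3 and 6. The rank sums are 123, 146 and 169 whatever k is. Friedman = 12/(73 × 3 × 4) × (123² + 146² + 169²) − 3 × 73 × 4 = 14.49, p = 0.0007 each time. Wilcoxon also stays at p = 0.007.

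**6. What a mean change would show.** The 95% CI half-width is t(0.975, 72) × SD/√73. For a change SD of 6, 8, 10 or 12 it is 1.4, 1.9, 2.3 or 2.8 points, all below 3.

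**The case against.** The other side has a good case on size.

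- **Power.** A reader might infer that the pre-test takes SDMT power from 84% to 63%. It does not. The lower figure assumes Friedman is always used, whereas a normal SDMT reaches it in about one trial in seven. The higher figure is a two-visit contrast set against three-visit omnibus tests, and that gap exists without any pre-test.
- **Follow-up test.** Section 9.4.3.2 provides Wilcoxon for Month 24 versus baseline, with nearly the power of the paired t test.
- **False positives.** A reader might suspect that a data-driven choice inflates the error rate. The simulations show it near 5%.
- **Effect estimate.** A reader might infer that the ANOVA branch would deliver the 3-point comparison and the pre-test removes it. Section 9.4.3.2 asks for no change estimate on either branch, and ANOVA tests equality across visits, not 3 points. Visit means with CIs are listed under Descriptive Statistics whichever branch is taken, so a difference can be read off, but without a paired CI.
- **What is tested.** The plan does not say that raw scores are tested, and the glossary's definition of a variable would admit a change score. Scores remain the likelier reading because scores are what section 9.4.3.2 compares.
- **The 3 points.** They are described as meaningful and expected, not as a success threshold, and for SDMT only.

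These objections limit the harm. They do not supply the missing decision rule, make the score distribution the right thing to test, or produce a mean change.

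**Conclusion.** The point holds as a defect of specification and reporting. The primary method depends on a preliminary test whose object and deciding visit are not stated and which, on the natural reading, looks at scores when changes matter. The three BICAMS scores can end up with different methods by chance. Where the rank branch is taken, there is no mean change to set against the 3-point SDMT gain; the ANOVA branch omits it too, so removing the pre-test alone would not be enough.

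The statistical cost is small for SDMT (about 2 power points) and larger, up to about 11, for a BVMTR score near its ceiling. The results do not support a claim of inflated type I error or of a large loss of SDMT power. All rates rest on assumed SDs, shapes and a correlation of 0.75. The BVMTR rates move widely with these assumptions. The undefined rule and the missing estimate do not depend on them.

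**What to change.** In sections 9.4.3.1 and 9.4.3.2, remove the Shapiro-Wilk switch for the BICAMS scores. Keep the repeated measures comparison of baseline, Month 12 and Month 24, which sections 2.3.1 and 9.4.3.2 both require, whatever the normality result. For each score, name the mean Month 24 minus baseline change, and the mean Month 12 minus baseline change, with paired 95% CIs as the effect estimates. Check the differences graphically. Report Friedman with Wilcoxon signed rank as a sensitivity analysis. Make the same change for PASAT, Stroop and MRI under Secondary Objectives in section 9.4.3.2.

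The cost is minor rewording of the analysis sections and one sensitivity analysis. No extra patients, visits or data are needed.
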